10.5.4.3. Supplementary Analysis

A supplementary analysis for the primary efficacy variable (defined in the supplementary estimand) will be performed using a logistic regression model fit separately to each indication with the following fixed effects: dose (as categorical variable), previous exposure to advanced IBD therapy (yes/no), and baseline modified Mayo score (UC patients) or SES-CD (CD patients). Each comparison of TEV-48574 dose versus placebo will be tested (one-sided) at a nominal significance level of $\alpha=0.1$.

In addition, a Cochran-Mantel-Haenszel (CMH) test for pairwise comparisons between the active dose groups and placebo will be performed separately for UC and CD. Nominal p-values will be presented for each of the comparisons.

10.5.4.4. Secondary Efficacy Analysis

All secondary efficacy endpoints will be analyzed separately for the UC and CD indications. For each binary endpoint, a logistic regression model similar to the supplementary model described in Section [10.5.4.3](#) with the respective baseline measurement will be used. For each comparison of TEV-48574 dose versus placebo, the differences in proportions, odds ratios, associated 95% CIs, and nominal p-value will be reported.

10.5.4.5. Other Efficacy Analysis

Consistency of treatment effect across baseline, demographic covariates, and subgroups may be explored. The variables, corresponding models, and relevant details will be pre-specified in the Statistical Analysis Plan.

10.6. Multiple Comparisons and Multiplicity

No adjustments to control the false-positive rate will be made for the preplanned multiple comparisons/endpoints analyses for the protocol-specified endpoints.

10.7. Safety Analysis

Safety analyses will be performed on the safety analysis set (Section [10.2.3](#)).

Safety assessments and time points are provided in [Table 1](#).

All adverse events will be coded using the Medical Dictionary for Regulatory Activities. Each patient will be counted only once in each preferred term or system organ class category for the

analyses of safety. Summaries will be presented for all adverse events (overall and by severity), adverse events determined by the investigator to be related to test IMP and/or device (ie, reasonable possibility) (defined as related or with missing relationship) (overall and by severity), serious adverse events, serious adverse device effects, and adverse events and adverse device effects causing withdrawal from the study. Summaries will be presented by treatment group, underlying disease, and for all patients. Patient listings of serious adverse events, serious adverse device effects, and adverse events and adverse device effects leading to withdrawal will be presented.

The frequency of each score measuring local tolerability, including an NRS-11 for pain intensity, at the injection site(s) will be listed and summarized for each time point.

Changes in laboratory, ECG, and vital signs measurements data will be summarized descriptively. Values will be compared with predefined criteria to identify potentially clinically significant values or changes, and such values will be listed.

The use of concomitant medications will be summarized by therapeutic class using descriptive statistics.

For continuous variables, descriptive statistics (number [n], mean, standard deviation, median, minimum, and maximum) will be provided for actual values and change from baseline to each time point. For categorical variables, patient counts and percentages will be provided.

If any patient dies during the study, a listing of deaths will be provided, and all relevant information will be discussed in the patient narrative included in the CSR.

10.8. Tolerability Analysis

Tolerability will be assessed by the number (%) of patients who fail to complete the study due to adverse events.

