	
CD:
 
 • Clinical response defined as a ≥ 100-point decrease in Crohn's Disease Activity Index (CDAI) score from baseline at weeks 4, 8, 12 and 14 • Clinical remission defined as a CDAI score < 150 at week 14 • Clinical response defined as a decrease from baseline of at least 50% in PRO2 (PRO2 is defined as having 2 components, abdominal pain and stool frequency) at week 14 • Clinical remission defined as abdominal pain ≤ 1 and stool frequency ≤ 3 on the PRO2 scale at week 14 • Endoscopic response defined as a decrease in modified multiplier (MM)-SES-CD of $> 50\%$ from baseline at week 14

A secondary objective of the study is to evaluate the safety and tolerability of 2 different doses of TEV-48574 sc administered Q2W in adult patients with IBD (moderate to severe UC or CD).
	
 • Adverse events • Change from baseline in clinical laboratory test results (serum chemistry, hematology, and urinalysis) • Change from baseline in vital signs measurements (blood pressure, pulse rate, body temperature, and respiratory rate) • Change from baseline in 12-lead electrocardiogram (ECG) findings • Patients who stopped the investigational medicinal product (IMP) due to adverse events • Local tolerability at the injection site

A secondary objective of the study is to evaluate the immunogenicity of 2 different doses of TEV-48574 sc administered Q2W in adult patients with IBD (moderate to severe UC or CD).
	
 • Change from baseline in treatment-emergent anti-drug antibody (ADA) at weeks 2, 4, 8, 14, and follow-up visit • Presence of neutralizing ADA in ADA positive patients at weeks 2, 4, 8, 14, and follow-up visit

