
A secondary objective of the study is to evaluate the safety and tolerability of 2 different doses of TEV-48574 sc administered Q2W in adult patients with IBD (moderate to severe UC or CD).
	
The safety and tolerability measures/parameters are as follows:
 
 • Adverse events • Change from baseline in clinical laboratory test results (serum chemistry, hematology, and urinalysis) • Change from baseline in vital signs measurements (blood pressure, pulse rate, body temperature, and respiratory rate) • Change from baseline in 12-lead electrocardiogram findings • Patients who stopped the investigational medicinal product due to adverse events • Local tolerability at the injection site

A secondary objective of the study is to evaluate the immunogenicity of 2 different doses of TEV-48574 sc administered Q2W in adult patients with IBD (moderate to severe UC or CD).
	
The immunogenicity endpoints for this study are as follows:
 
 • Change from baseline in treatment-emergent anti-drug antibody (ADA) at weeks 2, 4, 8, 14, and follow-up visit • Presence of neutralizing ADA in ADA positive patients at weeks 2, 4, 8, 14, and follow-up visit

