Patients randomized prior to Amendment 03 with Revision 01 will continue to receive the same dose, volume, and rate of administration of the IMP to which they were initially randomized and will remain blinded.

Treatment and Follow-Up Period: During the 14-week treatment period, patients will visit the site Q2W on days 1, 15, 29, 43, 57, 71, and 85 (± 3 days) for IMP administration (7 visits), as well as an end-of-treatment visit on day 99 (± 3 days; week 14) ([Table 1](#)). After the end of the

14-week treatment period, all patients may be offered the option to enter a long-term extension study, which is described in a separate protocol (TV48574-IMM-20038). If they choose to enter (sign the extension study informed consent form [ICF]) and will subsequently be randomized into the long-term extension study, they will not need to complete the follow-up visit in this study. All other patients will return to the site for a follow-up visit (day 127 [± 3 days]). For those patients who enter the long-term extension study, adverse events and concomitant medication data will be recorded in the dose-ranging study case report form (CRF) up until the date of extension study randomization (defined as the study completion date for the dose-ranging study). For those patients who screen fail the long-term extension study, adverse events and concomitant medication data will be recorded in the dose-ranging study up until the follow-up visit (day 127 [± 3 days]) CRF. Patients who complete the last scheduled visit will be considered to have completed the study.

Patients who withdraw from the study before completing the 14-week treatment period will complete the assessments for the early termination visit and will be encouraged to complete the follow-up period in the study.

The end of study is defined as the last visit of the last patient.

The total duration of patient participation in the study is planned to be up to 24 weeks for each individual patient.

The study duration will be approximately 27 months, from Q3 2022 until approximately Q4 2024.

Study procedures and assessments with respective time points are shown in [Table 1](#).

The overall study schematic diagram is shown in [Figure 1](#).

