4.4. Stopping Rules for the Study

4.4.1. Individual Stopping Criteria

4.4.1.1. Permanent Individual Withdrawn from IMP

IMP will be discontinued in the event of any of the following:

- The patient develops a serious or severe infection that is:
 - Life threatening

- Requires intensive care unit admission
 - Systemic opportunistic infection including tuberculosis (including pulmonary), cytomegalovirus (CMV; including CMV colitis), and listeriosis
- The patient experiences a serious or severe hypersensitivity reaction following investigational medicinal product (IMP) administration, meeting the Common Terminology Criteria for Adverse Events (CTCAE) criteria 3 to 4:
 - Anaphylaxis
 - Allergic reaction
 - Serum sickness
- The patient experiences a serious or severe Cytokine Release Syndrome following IMP administration, defined as CTCAE grade 3 to 4.
- The patient is diagnosed with malignant neoplasm other than appropriately treated basal cell carcinoma or squamous cell carcinoma of the skin or in situ carcinoma of uterine cervix.
- The patient experiences a serious adverse event where in the investigator, after consultation with the study sponsor's medical expert, assesses there is a reasonable possibility that the serious adverse event may be caused by the IMP.
- The patient becomes pregnant (see Section 8.3).
- The patient requires prohibited medications or an increase from baseline of the medications for the treatment of UC and CD, including surgery for UC and CD (see Section 6.6.3 and Section 6.6.4).
- Neutrophil count of:
 - Absolute neutrophil count $<0.5 \times 10^9/L$ confirmed on repeat testing within 3 to 5 days
 - Absolute neutrophil count $<1.0 \times 10^9/L$ that lasts for 2 weeks (retested every 3 to 5 days) or accompanied by fever $\geq 38.5^\circ\text{C}$
- Lymphocyte count:
 - Lymphocyte count $<0.2 \times 10^9/L$ confirmed on repeat testing within 3 to 5 days
 - Lymphocyte count 0.2 to $0.5 \times 10^9/L$ that lasts for 2 weeks (retested every 3 to 5 days)
- Hemoglobin $<8 \text{ g/dL}$ or an absolute decrease of $\geq 3 \text{ g/dL}$ from baseline (confirmed in repeated test)
- Platelets $<50 \times 10^9/L$ (confirmed in repeated test)
- Liver Chemistry Stopping and Increased monitoring criteria
 - (Refer to Liver Safety Required Actions and Follow up Assessments section in [Appendix K](#))

- alanine aminotransferase (ALT) or aspartate aminotransferase (AST) $\geq 5x$ upper limit of normal (ULN)

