5.3. Withdrawal Criteria and Assessments/Procedures for the Patient

In accordance with the Declaration of Helsinki (in accordance with the applicable country's acceptance), patients may completely withdraw from the study (ie, with no further study participation or contact) at any time for any reason. Patients may also discontinue IMP and remain in the study for assessments after consultation with the investigator and/or sponsor. The investigator and/or sponsor may also discontinue a patient from IMP and/or withdraw a patient from the study in any of the following events:

- in the event of intercurrent illness, adverse events, pregnancy, or any other reason concerning the health or well-being of the patient that indicates to the investigator that continued participation is not in the best interest of the patient (see also Individual Stopping Rules can be found in Section 4.4.1);
- if the patient is noncompliant with the study procedures and assessments or protocol-defined study restrictions or prohibited concomitant medication

Patients who terminate the study should complete the safety and efficacy evaluations specified for early termination in the Study Procedures and Assessments schedule ([Table 1](#)) at the time they terminate study participation, and they will be encouraged to complete the follow-up period in the study.

Investigators are to discuss patients who may be considering discontinuing IMP or withdrawing completely from the study with the sponsor as soon as the site becomes aware of the situation.

Investigators should attempt to obtain information on patients in the case of withdrawal from the study or discontinuation from IMP. Results of any evaluations and observations, together with a narrative describing the reason(s) for withdrawal from the study or discontinuation from IMP, should be recorded in the source documents. The CRF should document the primary reason for withdrawal from the study or discontinuation from IMP.

See [Appendix E](#) for information regarding how the study will define and address lost to follow-up patients to help limit the amount and impact of missing data.

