APPENDIX K. LIVER SAFETY: REQUIRED ACTIONS AND FOLLOW-UP ASSESSMENTS GUIDELINES

The liver chemistry stopping and increased monitoring criteria (see Section 4.4.1) have been designed to assure patient safety and evaluate liver event etiology and require follow up assessments as detailed below:

Required Actions and Follow up Assessments	
Actions	Follow up Assessment

 ○ Withhold study drug. ○ Report the event to Sponsor within 24 hours ○ Complete the liver event CRF and complete an SAE/PDAESI form. ○ Perform liver chemistry event follow-up assessments. ○ Monitor the patient and repeat liver chemistries (include ALT, AST, alkaline phosphatase, bilirubin and INR) weekly (if bilirubin >2x ULN or INR>1.5, twice weekly) until liver chemistries resolve, stabilize or return to within baseline ○ Do not restart/patient with study drug unless allowed per protocol and Sponsor approval is granted. ○ If restart is not allowed per protocol or not granted, permanently discontinue study treatment and complete the assessments for the early termination visit and the follow-up period in the study. 	
 ○ Viral hepatitis serology¹ ○ Obtain INR. ○ Obtain blood sample for pharmacokinetic analysis, as soon as possible, and at least within 7 days. ○ Obtain complete blood count with differential to assess eosinophilia. ○ Record the appearance or worsening of clinical symptoms of liver injury, or hypersensitivity, on the AE report form. ○ Record use of concomitant medications on the concomitant medications report form including acetaminophen, herbal remedies, other over the counter medications. ○ Record alcohol use on the liver event CRF ○ If bilirubin and/or INR are elevated: 
 ■ Test Anti-nuclear antibody, anti-smooth muscle antibody, Type 1 anti-live kidney microsomal antibodies, and quantitative total immunoglobulin G (IgG) or gamma globulins. ■ Check serum acetaminophen levels if definite or likely acetaminophen use in the preceding week: ■ Liver imaging (ultrasound, magnetic resonance, or computerized tomography) and/or liver biopsy. ■ Consider a specialist or hepatology consultation.

¹Includes: Hepatitis A immunoglobulin M (IgM) antibody; HBsAg and HBcAb; Hepatitis C RNA; Cytomegalovirus IgM antibody; Epstein-Barr viral capsid antigen IgM antibody (or if unavailable, obtain heterophile antibody or monospot testing); Hepatitis E IgM antibody.

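### The tolerability analysis counts adverse-event failures to complete the study, but the declared endpoint is stopping IMP for adverse events, so patients who stop drug and stay to the last visit are left out

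*Protocol*

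**What the plan says.** All references are to the protocol.

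- **Endpoint.** Section 3.1 lists, under the secondary safety and tolerability objective, "Patients who stopped the investigational medicinal product due to adverse events". The synopsis (Section 1.1) has the same item: "Patients who stopped the investigational medicinal product (IMP) due to adverse events".
- **Tolerability analysis.** Section 10.8 reads in full: "Tolerability will be assessed by the number (%) of patients who fail to complete the study due to adverse events".
- **Safety analysis.** The summaries in Section 10.7 include "adverse events and adverse device effects causing withdrawal from the study". No summary of events leading to IMP discontinuation is named.
- **Stopping drug versus leaving the study.** Section 5.3: "Patients may also discontinue IMP and remain in the study for assessments after consultation with the investigator and/or sponsor". The individual stopping rules in Section 4.4.1.1 act on the drug: "IMP will be discontinued in the event of any of the following".
- **Completion.** Section 4.1: "Patients who complete the last scheduled visit will be considered to have completed the study". No condition on completing IMP is attached.
- **Disposition.** Section 10.4.1 summarizes, as separate categories, patients who complete the study, withdraw from it and discontinue IMP. It breaks down withdrawals and IMP discontinuations by reason. Section 10.4 puts these summaries on the ITT set.

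**The concern.** The endpoint and its analysis name two different events, and the protocol itself keeps those events apart. The Section 10.8 count depends on two things: how many patients stop drug because of an adverse event, and how many of those then leave the study. Only the first is tolerability. Two arms with the same adverse-event stopping rate could report different tolerability figures because retention after stopping differed.

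Tolerability of the two doses is a stated secondary objective. As written, neither the section headed as the tolerability analysis nor the summary list in Section 10.7 analyses the declared endpoint.

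**Working it through.** No sample size, error rate or model is involved, and the plan gives no figure to reproduce. The check is to follow the definitions.

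**Step 1. Are the two events the same under this protocol?** No. Section 5.3 provides for stopping IMP while remaining in the study, Section 4.4.1.1 discontinues IMP without ending participation, and Section 10.4.1 treats study withdrawal and IMP discontinuation as separate categories.

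**Step 2. Classify each kind of patient who stops IMP for an adverse event.**

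| Patient | Declared endpoint (3.1) | Section 10.8 count |
|---|---|---|
| Stops IMP and leaves the study without attending the last scheduled visit | Counted | Counted |
| Stops IMP, remains under Section 5.3, attends the last scheduled visit | Counted | Not counted: a completer under Section 4.1 |
| Stops IMP, attends the early termination visit, then attends follow-up | Counted | Unclear |

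The third row is unclear for a reason in the text. Sections 4.1 and 5.3 describe patients who attend the early termination visit as having withdrawn from, or terminated, the study, and then encourage them to finish follow-up. Appendix K sends certain liver cases the same way: "permanently discontinue study treatment and complete the assessments for the early termination visit and the follow-up period in the study". Nothing says whether later attendance at week 18 restores completer status under the last-scheduled-visit sentence.

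**Step 3. Size.** Let S be the number of patients who stop IMP for an adverse event and C the number of those who still count as completers. Section 10.8 reports S − C, so the undercount is C, with 0 ≤ C ≤ S. The protocol gives neither S nor C.

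For illustration only, assume S = 6 among the 80 patients planned per dose (40 UC + 40 CD, Table 2). The 6 is an assumption and appears nowhere in the protocol.

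- Endpoint rate: 6/80 = 7.5%.
- Section 10.8 rate if C = 0: 6/80 = 7.5%.
- If C = 3: 3/80 = 3.75%.
- If C = 6: 0/80 = 0%.

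**Step 4. Is the right count available elsewhere?** Yes, in disposition. A patient who never received a dose cannot stop IMP, so apart from dosing errors the ITT disposition count and a safety-set count should agree in the numerator. The denominators may differ slightly, and the ITT set groups by randomized arm where the safety set groups by treatment received.

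**The case against.** The strongest reply is that this is a wording slip in a descriptive summary with little practical effect.

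- **The data are reported anyway.** Section 10.4.1 tabulates IMP discontinuation by reason, and Section 10.4 presents it by treatment group and by indication. This stands. A reader might infer that excess stopping on active drug would be hidden; the protocol does not support that. What disposition does not show is which adverse events led to stopping.
- **Early-termination patients may already be counted.** This also stands. A reader might take every early leaver who attends follow-up, and every Appendix K liver case, as missed. The text describes early-termination patients as having left the study, so they may be in the count. The firm gap is the patient who stops and stays under Section 5.3.
- **The completion sentence had another purpose.** The amendment history says it was reworded for patients rolling into the extension study. It is nonetheless the protocol's current definition of completion.
- **Other safety output covers these events.** Section 10.7 summarizes all, related and serious adverse events, and local tolerability separately. Its listings refer to events leading to withdrawal without adding that this means from the study, so they could be read to include IMP withdrawal. The preceding summary does specify the study. The whole tolerability assessment therefore does not rest on Section 10.8.
- **Few events are likely.** The Phase 1 study reported no withdrawals due to adverse events and the Phase 2a study no early terminations due to them. That suggests small numbers, but those studies were in healthy volunteers and asthma patients, and they do not separately report stopping IMP while staying in the study.
- **The SAP could handle it.** An extra table could be left to the SAP. The Section 10.8 variable could not: the protocol fixes it, and fixes it differently from its own endpoint.

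**Conclusion.** The inconsistency is real and lies within the protocol. The declared endpoint is stopping IMP due to adverse events; Section 10.8 analyses failure to complete the study, and the Section 10.7 summary uses study withdrawal. Patients who stop IMP for an adverse event, remain in the study and attend the last scheduled visit are left out of the designated tolerability count. This conclusion rests only on Sections 3.1, 4.1, 5.3 and 10.8 as written.

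The status of early-termination patients who later attend follow-up, including the Appendix K liver cases, is ambiguous and should not be claimed either way. The size of the undercount cannot be derived from the documents. The consequence is limited: the number can be recovered from disposition, and no efficacy result or decision rule depends on it. It is still worth correcting, because the analysis named for the objective should measure the endpoint named for it.

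**What to change.** - **Section 10.8:** define tolerability as the number (%) of patients in the safety analysis set who permanently discontinue IMP due to adverse events.
- **Section 10.7:** summarize and list adverse events leading to IMP discontinuation, and keep adverse events leading to study withdrawal as a separate line.

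This also removes the early-termination ambiguity from the tolerability measure, because completer status no longer enters it.

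The cost is a sentence in each section and one extra summary. Under Section 5.3 the CRF already documents the primary reason for stopping IMP or leaving the study, so no new data or visits are needed. No stopping rule or dose is affected. The reported rate may look slightly less favourable than under the present wording.
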